7.2.7 Dose preparation

Personnel should use appropriate protective clothing and equipment during syringe filling and application to prevent contamination with the radioactive solution (medical gloves / protective glasses). The individual responsible for study drug preparation will draw the correct volume of study drug into a syringe. The size of the syringe should be chosen according to the applied volume to reach the required dosing accuracy. Radium Ra-223 dichloride should not be diluted or mixed with any solutions. Do not store above 40°C (104°F). If the vials have been stored in a refrigerator, they should be left at room temperature for 1 hour prior to use, since cold material should not be injected into a patient. Store Radium Ra-223 dichloride in the original container or equivalent radiation shielding. This preparation is approved for use by persons under license by the Nuclear Regulatory Commission or the relevant regulatory authority of an Agreement State.

7.2.8 Dose administration

Before administration of study drug, the patient must be well hydrated; the patient should be instructed to drink ad libitum. Aseptic technique should be used in the administration of Radium Ra-223 dichloride. The syringe should be handed over to the individual who will perform the injection. The study medication will be administered by intravenous (IV) injection over 1 minute). After administration, the equipment used in connection with the preparation and administration of drug is to be treated as radioactive waste and should be disposed in accordance with local procedure for the handling of radioactive material.

7.3 Prohibited Concomitant Medications

- Concurrent anti-cancer therapy (chemotherapy, androgen deprivation therapy, immunotherapy, biologic therapy, or tumor embolization) other than Ra-223 dichloride and external beam radiation as specified in this protocol.
- Prior use of Radium-223 dichloride.
- Concurrent use of another investigational cytotoxic drug or cytotoxic device therapy (i.e., outside of study treatment) during, or within 4 weeks of trial entry (signing of the informed consent form). However, concomitant use of FDA approved nuclear medicine imaging agents (e.g., Fluciclovine, Choline C-11) used in an investigational imaging context will not be considered a contraindication to enrolling or continuing participation in the study.
- Major surgery within 30 days prior to start of study drug.

7.4 Duration of Therapy

Subjects must be withdrawn from the study treatment for the following reasons:

Patients are expected to receive one neo-adjuvant dose of Radium-223 followed by EBRT for 2 to 6 weeks followed by 5 additional cycles of Radium-223. The treatment phase of the study should be completed in approximately 6 months pending dose delay or discontinuation

- Subject withdraws consent from the study treatment and/or study procedures. A subject must be removed from the trial at his/her own request or at the request of his/her legally acceptable representative. At any time during the trial and without giving reasons, a subject may decline to participate further. The subject will not suffer any disadvantage as a result.
- Subject is lost to follow-up.
- Death.
- Disease progression as defined in section 10

- In the event of disease progression, the subject will no longer receive study treatment, but will remain on the study for all follow-up evaluations, which include indicated imaging studies, lab draws, and all questionnaires.

Subjects may be withdrawn from the study for the following reasons:

- The subject is non-compliant with study drug, trial procedures, or both; including the use of anti-cancer therapy not prescribed by the study protocol.
- If, in the investigator's opinion, continuation of the trial would be harmful to the subject's well-being.
- The development of a second cancer.
- Development of an intercurrent illness or situation which would, in the judgment of the investigator, significantly affect assessments of clinical status and trial endpoints.
- Deterioration of ECOG performance status to 4.

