3.1.3 Preclinical

In single and repeated dose toxicity studies in rats, the main findings were reduced body weight gain, hematological changes, reduced serum alkaline phosphatase and microscopic findings in the bone marrow (depletion of hematopoietic cells, fibrosis), spleen (secondary extra-medullary hematopoiesis) and bone (depletion of osteocytes, osteoblasts, osteoclasts, fibro-osseous lesions,

disruption/disorganization of the physis/growth line). These findings were related to radiation-induced impairment of hematopoiesis and a reduction of osteogenesis and occurred beginning in the dose range of 20 (0.00056 mCi) – 80 kBq (0.0022 mCi) per kg body weight, with the exception of body weight decreases.

Dose-limiting myelotoxicity was seen in dogs after single administration of 450 kBq (0.012 mCi) Radium Ra-223 dichloride per kg body weight (9 times the clinically recommended dose).

Osteosarcomas, a known effect of bone-seeking radionuclides, were observed at clinically relevant doses in rats 7 to 12 months after start of treatment.

Osteosarcomas were not observed in dog studies. The presence of neoplastic changes, other than osteosarcomas, was also reported in the longer term (12 to 15 months) rat toxicity studies. Due to its mode of action, and as seen with conventional radiotherapy and other radiotherapeutics, Radium-223 dichloride may have the potential to induce secondary malignancies. No case of osteosarcoma has been reported in clinical studies with Radium Ra-223 dichloride. The risk for patients to develop osteosarcomas with exposure to Radium Ra-223 dichloride is unknown at present.

Studies on reproductive and developmental toxicity have not been performed. Since Radium Ra-223 dichloride binds to bone, the potential risk for toxic effects in the male gonads in cancer patients with castration-resistant prostate cancer is very low, but cannot be excluded. Studies on the mutagenic and carcinogenic potential of Radium Ra-223 dichloride have not been performed.

No histological changes were observed in organs involved in the excretion of Radium Ra-223 dichloride. No significant effects were seen on vital organ systems, i.e., cardiovascular (dog), respiratory or central nervous systems (rat), after single dose administration of 450 to 1000 kBq (0.012 to 0.027 mCi) per kg body weight (9 (dog) to 20 (rat) times the clinically recommended dose.

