No cases of radiation-induced cancer have been reported in reported in clinical trials with Radium-223 dichloride in follow-up of up to three years. However, the radiation dose resulting from therapeutic exposure may result in higher incidence of cancer (e.g., sarcomas of the bone, or leukemia), mutations and a potential for development of hereditary defects.

Bone Marrow Suppression

In the randomized trial, 2% of patients on the Radium Ra-223 dichloride arm experienced bone marrow failure or ongoing pancytopenia compared to no patients treated with placebo. There were two deaths due to bone marrow failure and for 7 of 13 patients treated with Radium Ra-223 dichloride, bone marrow failure was ongoing at the time of death. Among the 13 patients who experienced bone marrow failure, 54% required blood transfusions. Four percent (4%) of patients on the Radium Ra-223 dichloride arm and 2% on the placebo arm permanently discontinued therapy due to bone marrow suppression.

In the randomized trial, deaths related to vascular hemorrhage in association with myelosuppression were observed in 1% of Radium Ra-223 dichloride-treated

patients compared to 0.3% of patients treated with placebo. The incidence of infection-related deaths (2%), serious infections (10%), and febrile neutropenia (<1%) were similar for patients treated with Radium Ra-223 dichloride and placebo.

Myelosuppression; notably thrombocytopenia, neutropenia, pancytopenia, and leukopenia; has been reported in patients treated with Radium Ra-223 dichloride. In the randomized trial, complete blood counts (CBCs) were obtained every 4 weeks prior to each dose and the nadir CBCs and times of recovery were not well characterized. In a separate single-dose phase 1 study of Radium Ra-223 dichloride, neutrophil and platelet count nadirs occurred 2 to 3 weeks after Radium Ra-223 dichloride administration at doses that were up to 1 to 5 times the recommended dose, and most patients recovered approximately 6 to 8 weeks after administration.

In the Radium-233 arm of the Phase 3 clinical trial reported in Parker et al. (2013) 12.7% (76/600) of subjects had grade 3+ anemia, 6.5% (39/600) of subjects had grade 3+ thrombocytopenia, and 2.2% (13/600) of subjects had grade 3+ neutropenia.

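### Section 7.4 allows withdrawal from the study itself for a second cancer, ECOG 4 and other grounds with no provision for continued follow-up, in conflict with the planned 15-month and two-year observation

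*Combined protocol and SAP*

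**What the plan says.** Section 7.4 contains two lists with different objects.

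- The first opens "Subjects must be withdrawn from the study treatment for the following reasons". It covers withdrawal of consent, loss to follow-up, death and disease progression. For progression alone it adds that the man stops treatment but "will remain on the study for all follow-up evaluations".
- The second opens "Subjects may be withdrawn from the study for the following reasons". It covers non-compliance, "including the use of anti-cancer therapy not prescribed by the study protocol"; a judgement by the investigator that staying in would do the man harm; a new malignancy, worded as "The development of a second cancer"; an intercurrent illness that would affect clinical assessments and endpoints; and decline to ECOG 4. No sentence on continued follow-up is attached to this list.

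Other sections plan observation without exceptions. Sections 1.2.5 and 10 plan two years from enrollment, 10.1 follows men to the start of ADT, and section 11 plans the primary analysis at 15 months of follow-up for all enrollees. Section 7.3 classes ADT as anti-cancer therapy. On second cancers, section 3.1.3 says that "Radium-223 dichloride may have the potential to induce secondary malignancies", and section 3.1.4 says that the radiation dose "may result in higher incidence of cancer (e.g., sarcomas of the bone, or leukemia").

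**The concern.** Several grounds in the second list are linked to prognosis or to the outcomes being measured. Stopping treatment and stopping observation are separate decisions. Section 7.4 separates them for progression but not for the other grounds. If the discretion is used, three things are at stake:

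- **Primary endpoint.** A man withdrawn before 15 months and before any systemic therapy has unknown status, and the plan does not say how to count him.
- **Survival and skeletal events.** Section 11 analyses both by Kaplan-Meier, which assumes that censoring is unrelated to prognosis. Withdrawal for ECOG 4 or serious illness breaks that assumption.
- **Late safety.** Section 15.4.1 follows an adverse event until it resolves or until the man's participation ends. The course and outcome of a second cancer, and anything that occurs later, can go unrecorded.

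**Working it through.** **1. The passages side by side.** Take a man who progresses and then starts ADT. The progression sentence in 7.4 keeps him in follow-up. ADT is anti-cancer therapy under 7.3 and is not part of study treatment, so on a literal reading the second list lets him be withdrawn from the study. Both rules apply and nothing ranks them. Now take a man with a second cancer or ECOG 4 at month 9 who has not started systemic therapy. Sections 1.2.5, 10, 10.1 and 11 require his later data, while 7.4 lets him leave without giving them. The evaluability rule in section 10 does not settle his case, because it depends on treatment received, not on whether 15-month status is known.

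**2. The plan's own figures.** Inputs from section 11: n = 20; 1% free of systemic therapy under the null and 20% under the alternative; reject if 2 or more are free. The window is taken as 15 months, as in the hypotheses, although the sentence giving the rejection rule says one year.

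- Power = 1 − 0.80^20 − 20(0.20)(0.80^19) = 1 − 0.0115 − 0.0576 = 0.931. The stated 93% is reproduced.
- Type I error = 1 − 0.99^20 − 20(0.01)(0.99^19) = 0.0169, or 1.7%.

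**3. Men with unknown 15-month status.** Let k men be withdrawn before 15 months and before systemic therapy. The documents give no withdrawal rate and no allowance for one, so k is an assumption. The other 20 − k men are treated as independent with the rates above, and the cut-off stays at 2.

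| k | Excluded, or counted as having started therapy: power | Counted as free of therapy: type I error |
|---|---|---|
| 0 | 93.1% | 1.7% |
| 1 | 91.7% | 17.4% |
| 2 | 90.1% | 100% |
| 3 | 88.2% | 100% |
| 4 | 85.9% | 100% |

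For k = 1 counted as free, only one more success is needed among 19 men: 1 − 0.99^19 = 0.174. For k = 2 the cut-off is met before any other man is counted. For k = 2 excluded, power = 1 − 0.80^18 − 18(0.20)(0.80^17) = 0.901. Under exclusion the type I error stays at or below 1.7%.

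**4. Two-year survival, as an assumed example.** Suppose 4 of 20 men die by two years, and 2 of those 4 were first withdrawn and their deaths never ascertained.

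- Full follow-up: 16/20 = 80%.
- Both censored before the two observed deaths: (17/18)(16/17) = 88.9%.
- Both censored after them: (19/20)(18/19) = 90.0%.

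The comparator figure in section 2 is 85%, for minimal disease on intermittent ADT.

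**The case against.** The strongest reply is that the second list is permissive, sits under a heading about duration of therapy, and should be read in light of the unqualified follow-up commitments in sections 1.2.5, 10 and 10.1. That makes it a wording conflict, not a design that sets out to end observation. This is fair, and it is how the point is put here. It does not remove the conflict: the two lists name different objects, the retention sentence was written for one ground only, and discretion exercised on prognosis is itself a source of bias.

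Three stronger readings are tempting, and the documents do not support them.

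- A reader might infer that a second cancer would go uncounted. A man withdrawn because a second cancer was found is a known case, and 15.4.1 requires adverse events to be recorded immediately. What can be lost is its course and outcome, and later events.
- A reader might infer that the primary event is lost when a man starts ADT and is withdrawn for it. By then the event has been observed. The loss is in later survival, skeletal-event, quality-of-life and toxicity data.
- A reader might infer that 7.4 alone ends safety collection. Sections 15.4.1 and 15.4.2 already end collection of related events at the last study visit or at new cancer treatment, if sooner. All events are collected to 30 days after the last dose in any case, and 15.4.2 still requires reporting of later deaths felt to be treatment related.

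The survival example also has limits. With the 94% two-year survival quoted in section 2 for five or fewer bone lesions, 20 × 0.06 = 1.2 deaths are expected and the chance of 4 or more is about 3%. With 85% it is about 35%. Overall survival is descriptive, so crossing 85% triggers no decision. The direction of bias in time to first skeletal event is not shown for every ground; withdrawal for a second cancer has no obvious direction.

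**Conclusion.** The concern holds as an internal conflict that is worth correcting. Section 7.4 permits study withdrawal on prognosis-linked grounds without retaining those men, while other sections require their data to 15 months and two years. The clearest consequence is for the primary test. With a cut-off of 2 of 20 and no counting rule, one man of unknown status can move the type I error from 1.7% to 17.4% if he is counted as therapy-free, and two such men decide the result. Excluding them, or counting them as having started therapy, is much milder: power of 90% with two such men. The effect on survival (80% against 89–90% in the example) shows the mechanism and is not a forecast. All of these sizes depend on the discretion being used and on status not being obtained afterwards; the documents give no rate for either.

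**What to change.** Reconcile section 7.4 with sections 1.2.5, 10, 10.1 and 11 by extending the existing retention sentence to the second list, leaving every ground and every treatment rule as written. For men withdrawn on those grounds, continue the three-monthly visits in the study calendar and collect to two years:

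- the date of ADT or other systemic therapy;
- skeletal-related events;
- second-cancer outcome;
- survival status.

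The exceptions are withdrawal of consent to follow-up, loss to follow-up and death.

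In the same amendment, reconcile the clause in 15.4.1 and 15.4.2 that ends related AE and SAE collection at new cancer treatment. Otherwise the change to 7.4 will not secure late safety data for men who start such treatment.

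The cost is a short amendment touching 7.4, 15.4.1 and 15.4.2, plus continued contact with a few ill men, who may decline visits. The visits themselves are already scheduled.

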8 TOXICITIES AND DOSEAGE MODIFICATION

This study will utilize the CTCAE (NCI Common Terminology Criteria for Adverse Events) Version 4.0 for adverse event and serious adverse event reporting. A copy of the CTCAE Version 4.0 can be downloaded: (<http://safetyprofiler-ctep.nci.nih.gov/CTC/CTC.aspx>).

8.1 Dose Modifications

8.1.1 Dose Modification

Every effort should be made to administer the full dosing regimen of Radium Ra-223 dichloride. Adjustment of dose level is not permitted.

Study visits for administration of Radium-223 during the treatment period should occur at 28 day intervals (within a window of 0 and +14 days). Radium-223 cannot be administered earlier than 28 days from the previous administration. Dosing delays may be instituted under the following circumstances:

Disease progression:

The Investigator should delay cytotoxic chemotherapy, other systemic radioisotope, hemibody external radiotherapy or other investigational drug until the follow-up period. If such treatments have to be given during the treatment period, further study drug administrations must be discontinued.

Patients with a single PSA result that meets biochemical progression criteria may continue on treatment, at the investigator's discretion, until a confirmatory PSA result is returned. Upon confirmed biochemical progression study treatment MUST be discontinued.

Patients who demonstrate radiographic or clinical progression must discontinue study treatment.

Myelosuppression:

Treatment-related changes in hematology parameters may occur.

- If a patient experiences CTCAE v4.03 Grade 3 or 4 neutropenia, thrombocytopenia, or anemia the administration of study drug should be delayed until recovery to Grade 2 or better.
- If a patient experiences CTCAE v4.03 Grade 3 or 4 neutropenia, thrombocytopenia, or anemia lasting > 14 days, further study drug administrations must be discontinued.
- Blood transfusion is acceptable between study drug administrations but not prior to the start of the study. Use of biologic response modifiers, such as G-CSF or GM-CSF, is allowed in the management of acute toxicity.
- Hematologic evaluation of patients must be performed at baseline and prior to every dose of Radium Ra-223 dichloride. Before the first administration of Radium Ra-223 dichloride, the absolute neutrophil count (ANC) should be $\geq 1.5 \times 10^9/L$, the platelet count $\geq 100 \times 10^9/L$ and hemoglobin $\geq 10 \text{ g/dL}$. Before subsequent administrations of Radium Ra-223 dichloride, the ANC should be $\geq 1.0 \times 10^9/L$ and the platelet count $\geq 50 \times 10^9/L$ and hemoglobin $\geq 9.0 \text{ g/dL}$. If there is no recovery to these values within 6 to 8 weeks after the last administration of Radium Ra-223 dichloride, despite receiving supportive care, further treatment with Radium Ra-223 dichloride should be discontinued. Patients with evidence of compromised bone marrow reserve should be monitored closely and provided with supportive care measures when clinically indicated. Discontinue Radium Ra-223 dichloride in patients who experience life-threatening complications despite supportive care for bone marrow failure.

Gastrointestinal events:

Diarrhea should be treated as per local practice. A further dose of study medication should not be given before diarrhea is recovered to CTCAE v4.03 Grade 2 or baseline levels.

Nausea or vomiting should be treated as per local practice. A further dose of study medication should not be given before nausea or vomiting is recovered to CTCAE v.4.03 Grade 2 or baseline levels.

Spinal Cord Compression:

If the patient experiences spinal cord compression during the treatment period, the patient should be treated for the event, and may receive further study drug administration if adequately recovered.

Surgical Intervention:

If surgery is required, the patient should continue with study treatment, if this is considered safe in the treating Investigator's opinion. The surgeon needs to be notified that the patient has been given radioactive drug, and needs to follow the guidelines for radioactive protection.

Non-pathological fractures:

For traumatic fractures in weight-bearing bones during treatment phase, the study drug administration should be delayed for 2 to 4 weeks from the time of fracture.

Pathological fractures:

Pathological fractures may occur as the result of either progressive disease or increased physical activity associated with significant pain palliation. Pathologic fractures are to be treated in a manner that attempts to maintain the best functional status and quality of life. Study treatment may continue as planned.

Any Other Toxicity:

Local practice will apply.

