Clinical Progression: the development of any skeletal related event defined as: time to any EBRT not required as a study procedure, time to first pathological bone fracture, time to spinal cord compression, or time to surgical intervention.

RECIST 1.1 and PCG 2 Assessments:

The following definitions and criteria for RECIST 1.1 and PCWG2 should be used for the baseline evaluations of existing disease and for the ongoing evaluation of tumor responses.

Measurable lesions - lesions that can be accurately measured in at least one dimension with longest diameter (LD) ≥ 10 mm using CT, MRI, or caliper measurements or ≥ 20 mm with x-ray.

Non-measurable lesions - all other lesions including small lesions (LD < 10 mm with CT, MRI, or caliper measurements or < 20 mm with x-ray).

Documentation of “Target” and “Non-Target” Lesions

- All measurable lesions up to a maximum of two lesions per organ and five lesions in total, representative of all involved organs should be identified as ***target lesions*** and recorded and measured at baseline.
- Target lesions should be selected on the basis of their size (lesions with the longest diameter) and their suitability for accurate repeated measurements (either by imaging techniques or clinical assessments).
- A sum of the LD for *all target lesions* will be calculated and reported as the baseline sum LD. The baseline sum LD will be used as the reference by which to characterize the objective tumor response.
- All other lesions (or sites of disease) should be identified as ***non-target lesions*** and should also be recorded at baseline. Measurements of these lesions are not required, but the presence or absence of each should be noted throughout follow-up.

RECIST Response Criteria

Evaluation of target lesions	
Complete Response (CR)	Disappearance of all target lesions (Must persist for a minimum of four weeks)
Partial Response (PR)	At least a 30% decrease in the sum of the LD of target lesions, taking as reference the baseline sum LD (Must persist for a minimum of four weeks)
Progressive Disease (PD)	At least a 20% increase in the sum of the LD of target lesions, taking as reference the smallest sum LD recorded since the treatment started or the appearance of one or more new lesions
Stable Disease (SD)	Neither sufficient shrinkage to qualify for PR nor sufficient increase to qualify for PD, taking as reference the smallest sum LD since the treatment started

Evaluation of non-target lesions	

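### From Cycle 2 on, pathological fracture and spinal cord compression carry both a mandatory stop of Radium-223 and a permission to continue it; skeletal surgery overlaps in the same way

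*Combined protocol and SAP*

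**What the plan says.** **Rules that stop treatment**

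- Protocol section 10.1 defines clinical progression as "the development of any skeletal related event defined as: time to any EBRT not required as a study procedure", and completes the list with "time to first pathological bone fracture, time to spinal cord compression, or time to surgical intervention". It starts to measure progression only once external beam radiotherapy (EBRT) is complete and Cycle 2 of Radium-223 has been given.
- Section 8.1.1, under disease progression: "Patients who demonstrate radiographic or clinical progression must discontinue study treatment".
- Section 7.4 gives one list of reasons for which study treatment must stop and a separate list for which a subject may be withdrawn. The mandatory list contains "Disease progression as defined in section 10", and the section adds: "In the event of disease progression, the subject will no longer receive study treatment, but will remain on the study for all follow-up evaluations".

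**Rules that let treatment go on, later in section 8.1.1**

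- Spinal cord compression during the treatment period: "the patient should be treated for the event, and may receive further study drug administration if adequately recovered".
- Surgery: "If surgery is required, the patient should continue with study treatment". The sentence goes on to make this conditional on the treating investigator judging it safe.
- Pathological fracture: "Study treatment may continue as planned". The same paragraph notes that such a fracture may reflect either progressive disease or greater activity after pain relief.

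**The concern.** For the same event in the same man, one part of section 8.1.1 (with section 7.4) orders Radium-223 to stop and another part of section 8.1.1 allows it to go on. An investigator who follows either instruction departs from the other.

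Two things are at stake. One is the conduct of treatment: whether a further dose of a radioactive drug is given after a cord compression or a pathological fracture is left contradictory. The other is the analysis set: the number of cycles a man receives decides whether he is evaluable under section 10, and section 11 bases its test on 20 evaluable subjects.

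**Working it through.** The point rests on the text, not on a figure. The one related figure in the plan is the power in section 11. With 20 evaluable men, rejection at 2 or more free of systemic therapy, and 20% free under the alternative, power is 1 − 0.80^20 − 20 × 0.20 × 0.80^19 = 1 − 0.0115 − 0.0576 = 0.931. The stated 93% therefore reproduces, and the contradiction does not alter it.

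**Step 1. Set the rules side by side, event by event.**

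| Event listed in 10.1 | 7.4 and 8.1.1 (progression) | 8.1.1 (event-specific) | Can both be followed? |
|---|---|---|---|
| Pathological fracture | Must stop | May continue; no condition | No, if treatment continues |
| Spinal cord compression | Must stop | May continue if adequately recovered | No, if treatment continues |
| Surgical intervention, skeletal | Must stop | Should continue if judged safe | No, when judged safe |
| EBRT outside the study | Must stop | No permission to continue found | Yes |

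That is two clear conflicts, one partial overlap (surgery) and one event without conflict.

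**Step 2. Look for a rule that settles the conflict.** No text says that the event-specific paragraphs override the progression rule, or the reverse. Section 8.1.1 does write an exception for one situation: a man with a single PSA result meeting the biochemical criteria may stay on treatment until the confirmatory result is back. There is no such exception for skeletal events. The conditions on continuing are recovery and safety; neither is absence of progression, so meeting them does not take the man out of the section 10.1 definition.

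**Step 3. Fix the time window.** Before EBRT is complete and Cycle 2 is given, section 10.1 does not yet measure progression, so the permissions apply without conflict. The cord compression permission covers the whole treatment period, and the surgery and pathological fracture permissions have no time limit. The conflict therefore runs from that point until Cycle 6; after Cycle 6 no dose is left to give or withhold.

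**Step 4. Follow the consequence for evaluability.** Section 10 requires Cycle 1, EBRT and at least 3 cycles of Radium-223. This can be read as 3 cycles in all, or as Cycle 1 plus 3 more (1 + 3 = 4).

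| Event falls between | Cycles received if stopped | Evaluable, 3 in all | Evaluable, 4 in all | Cycles possible if continued |
|---|---|---|---|---|
| Cycles 2 and 3 | 2 | No | No | 6 |
| Cycles 3 and 4 | 3 | Yes | No | 6 |
| Cycles 4 and 5 | 4 | Yes | Yes | 6 |
| Cycles 5 and 6 | 5 | Yes | Yes | 6 |

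So the choice of rule decides evaluability for an event between Cycles 2 and 3 on either reading, and between Cycles 3 and 4 on the stricter reading only.

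**The case against.** The strongest defence is that the specific paragraphs are meant to qualify the general one, that the conditions of recovery and safety protect the patient, and that section 7.4 separately lets the investigator withdraw a man for whom continuing would be harmful. That may be what was intended, but it is not written: sections 7.4 and 8.1.1 state the progression rule without discretion. The defence does narrow the point in three ways. Events before the section 10.1 window are not in conflict. Continuing after cord compression or surgery is conditional. And these events may be few, since men have at most five bone lesions and imminent cord compression is an exclusion.

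A reader might infer more than the documents support:

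- **That any operation counts as clinical progression.** Section 10.1 lists surgical intervention as a skeletal related event, and section 1.2.3 describes such events as complications of bone metastases. The surgery paragraph in 8.1.1 is general, so an operation unrelated to bone is not clearly in conflict.
- **That a man who continues Radium-223 is not counted as progressed.** Section 10.1 defines progression by the event itself. Dosing rules do not change its date, so progression-free survival and the exploratory assay correlations do not directly depend on which dosing rule is followed.
- **That the contradiction decides the primary result.** The endpoint is the start of androgen deprivation or other systemic therapy. Section 7.4 keeps progressed men in follow-up and does not require that therapy, so a route from stopping Radium-223 to endpoint failure would be an added assumption.

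**Conclusion.** The contradiction holds as written for pathological fracture and spinal cord compression, and partly for surgery, where it is limited to skeletal operations. It applies from completion of EBRT and delivery of Cycle 2 up to Cycle 6. A mandatory stop and an instruction or permission to continue cannot both be acted on.

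Its size can be stated only per man: the choice of rule can change the cycles he receives from as few as 2 to as many as 6, and with that his evaluability. The documents give no on-treatment rate for these events, so the number of men affected is unknown. No effect on the primary conclusion is claimed.

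The verdict assumes that the section 10.1 definition of progression is the one that sections 7.4 and 8.1.1 apply. Section 7.4 refers to section 10 explicitly; section 8.1.1 uses the same term without a cross-reference.

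**What to change.** Reconcile sections 7.4, 8.1.1 and 10.1 so that pathological fracture, spinal cord compression and skeletal surgery each have one stated consequence for study treatment. If one rule is meant to take precedence over another, say so in the text. Which consequence applies is for the sponsor to decide.

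Give surgical intervention in section 10.1 and surgery in section 8.1.1 a consistent stated scope, so that it is clear which operations each covers. The sponsor sets that scope as well.

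The cost is a wording amendment, with the usual ethics board submission. It needs no extra patients, visits or procedures.
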